The evolving understanding of pain physiology in children has led to advancements in multimodal analgesic techniques. Pain management plans encompass a spectrum of interventions ranging from medications, psychological support, and regional anaesthesia. Caudal anaesthesia is one of the most commonly performed regional anaesthesia techniques in paediatrics. A single dose of bupivacaine in the epidural space when accessed through the sacral hiatus provides analgesia for

almost the entirety of the surgical procedure time, but unfortunately, its action is time limited in the postoperative period. ⁽⁸⁾

An ultrasound guided technique has been proven to provide better accuracy and success rate along with decreased puncture rates and increased first puncture success rates compared to a blind caudal block. Transverse and longitudinal views using ultrasound illustrate the sacrococcygeal ligament, the two sacral cornua and the dura mater with epidural space. ^(9, 10)

Erector spinae block is a relatively new technique first described by Forero et al in 2016. Since then, it has been described as an effective block in the paediatric population. It effectively blocks somatic and visceral pain when administered correctly in thoracic or abdominal surgeries, unilaterally or bilaterally. ^(11, 12)

Its analgesic effect appears to be due to injecting local anaesthetic into the interfacial plane between the transversus process and erector spinae accompanied by diffusion into paravertebral and intercostal spaces, where it affects the ventral and dorsal rami of spinal nerves. ^(13, 14)

As the field continues to progress, ongoing research and clinical innovations aim to provide an effective approach to the well-being of young surgical recipients with the most amount of pain control. In this study, we hypothesize that, erector spinae block may be an alternative technique for caudal block for perioperative analgesia in children undergoing lower abdominal surgeries. Our aim will be to compare between erector spinae block and the caudal block to determine which one will provide better postoperative analgesia for a longer duration with fewer side effects.

AIM OF THE WORK

Primary aim: is to evaluate the efficacy of postoperative pain management using the Face, Legs, Activity, Cry, Conceal ability (FLACC) Pain Scale.

Secondary aim:

- Intraoperative haemodynamic changes.
- The time to first rescue analgesic.
- Total postoperative analgesic requirements.

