- Parent satisfaction with a 5-point Likert scale questionnaire. ⁽¹⁵⁾
- Number of patients required rescue analgesic postoperatively.
- Time to Modified Aldrete score ≥ 9 . ⁽¹⁶⁾
- PACU stay (min).
- Incidence of any adverse effects.

PATIENTS

After approval of the Medical Ethics Committee of the Faculty of Medicine, Alexandria University. An informed written consent from every patient from parent/caregiver will be done in this study, the current study will be performed in El Shatby University Hospital for children on 60 patients who will be scheduled for elective lower abdominal surgeries under general anaesthesia.

The minimum total hypothesized sample size of 60 eligible study participants will be needed to evaluate the efficacy of postoperative pain management using the Face, Legs, Activity, Cry, Consolability (FLACC) Pain Scale. Taking into consideration an effect size of 20%, significance level of 5% and power of 8-% using Chi Square Test.

This study will be a prospective randomized study. Randomization was done using a computer-generated random numbering of each study patient where even numbers will be group (ESB) and odd numbers will be group (CB). Opaque sealed envelopes will be used and will be opened in the operative theatre by an investigator who will be blinded to the study groups. The parents, children, surgeon, and the investigators who will collect the data after the block will be blinded to the study group. Patients will be randomized into two equal groups:

Group (ESPB): patients will receive bilateral ultrasound guided erector spinae block of dilute solution at dose 0.4 ml/kg of 0.25% bupivacaine between the 10th transversus process and erector spinae muscle on each side, provided that it does not exceed toxic dose of bupivacaine 2.5 mg/kg. ⁽¹⁷⁾

Group (CB): patients will receive ultrasound guided caudal epidural block of dilute solution bupivacaine 0.25% at dose 1ml/kg, provided that it does not exceed toxic dose of bupivacaine 2.5 mg/kg. ⁽¹⁸⁾

Inclusion criteria:

- Age between 2-7 years old.
- ASA I-II.
- Elective surgery under general anaesthesia.
- Lower abdominal surgery.

Exclusion criteria:

- Parent/caregiver refusal.
- Allergy to one of the study medications.
- Renal or cardiac disease.
- Infection or redness at the site of injection.
- Clinically significant coagulopathy.
- Spinal anomalies.
- Altered mental status.
- Developmental delay.
- Additional surgery at different surgical sites.
- Block failure.

METHODS

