Each category is scored on the 0–2 scale, which results in a total score of 0–10.

Table (2): Interpreting the FLACC Behavioural Score

0	Relaxed and comfortable
1–3	Mild Pain
4–6	Moderate pain
7–10	Severe Pain

6. Time to first postoperative analgesic request

The time elapsed between end of surgery and first administration of an analgesic.

A postoperative pain score of ≥ 4 will be managed with paracetamol 10 mg/kg intravenous then will be repeated every 6 hours as required.

If pain persists after dose of paracetamol or score >4 , nalbuphine will be given at dose 0.1 mg/kg intravenously.

7. Total postoperative analgesics requirement will be recorded.

8. Number of patients who will require postoperative rescue analgesia.

9. Parent satisfaction:

Parent satisfaction with a 5-point Likert scale questionnaire.

10. Side effects:

A) Side effects related to bupivacaine:

- **CNS:** Nausea, vomiting, circumoral numbness, facial tingling, vertigo, tinnitus, restlessness, anxiety, dizziness, seizure, coma.
- **Cardiovascular:** hypotension, arrhythmia, bradycardia, heart block, cardiac arrest.
- **Allergic reactions**

B) Side effects related to the erector spinae technique:

In addition to the common complications associated with any peripheral nerve block (local anaesthetic toxicity, intravascular injection, nerve injury, bleeding, and infection), vascular puncture, pleural puncture, pneumothorax, and failed block are the primary complications.

C) Side effects related to the caudal block technique:

Epidural abscess, meningitis, post dural puncture headache, subdural injection, pneumocephalus, air embolism and back pain.

ETHICS OF RESEARCH

Research on human or human products:

- Prospective study: Informed consent will be taken from patients. In case of incompetent patients, the informed consent will be taken from the guardians.
- Retrospective study: Confidentiality of records will be considered.
- DNA / genomic material: Informed consent for DNA / genomic test and for research will be taken from patients. No further tests will be carried out except with further approval of committee and patients. If the samples will travel outside Egypt the researcher will be responsible for transportation and security approval.
- All drugs used in the research are approved by the Egyptian Ministry of Health.

Research on animal:

- The animal species are appropriate for the test.
- After test, if the animal will suffer, it will be euthanized and properly disposed.

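### Two duration definitions are exchanged, and the rescue rule leaves open whether nalbuphine accompanies or follows paracetamol at a first FLACC score of 5 to 10

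*Protocol*

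**What the plan says.** **Durations.** Protocol, MEASUREMENTS, item 1 (Demographic data) defines two intervals in minutes. Duration of surgery runs from the beginning of induction until the inhaled agent is turned off. Duration of anaesthesia runs from incision to the closing skin suture. Under Block Procedure, both groups wait 10 minutes between the block and the start of surgery.

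**Rescue.** MEASUREMENTS, item 6 states: "A postoperative pain score of ≥ 4 will be managed with paracetamol 10 mg/kg intravenous", repeated 6-hourly as needed. The next sentence reads "If pain persists after dose of paracetamol or score >4", and then "nalbuphine will be given at dose 0.1 mg/kg intravenously". On the FLACC scale, "Each category is scored on the 0–2 scale, which results in a total score of 0–10".

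**Outcomes that this rule feeds.** The secondary aims include "Total postoperative analgesic requirements" and "Number of patients required rescue analgesic postoperatively". Item 7 of MEASUREMENTS repeats the first of these: "Total postoperative analgesics requirement will be recorded". Time to first analgesic is defined in item 6 as "The time elapsed between end of surgery and first administration of an analgesic".

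**The concern.** The duration definitions specify recorded variables. If the case-record form follows them, the table of patient characteristics reports an anaesthesia interval as surgery and a surgery interval as anaesthesia.

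The rescue sentences determine which drugs a child receives, and so generate the analgesic-requirement outcome. The first sentence has no upper score limit. In the second, a score above 4 can be read in two ways:

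- **Reading A:** it is a trigger in its own right, so a first score of 5 or more calls for nalbuphine together with the paracetamol already required.
- **Reading B:** it is a score that remains after paracetamol, so nalbuphine comes only later, if at all.

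The protocol gives no reassessment time after paracetamol and does not define persisting pain, so nothing elsewhere settles the order. The same first score can then produce different recorded nalbuphine, according to how staff read the rule. A statistical analysis plan could say how consumption is summarised, but it could not undo doses already given.

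**Working it through.** **Durations.** Let *a* be the start of induction, *b* the incision, *c* the final skin suture and *d* the moment the inhaled agent is stopped.

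- Surgery as written = *d* − *a*; anaesthesia as written = *c* − *b*.
- Surgery minus anaesthesia = (*b* − *a*) + (*d* − *c*).
- The block follows induction, and incision comes 10 minutes after the block in both groups, so *b* − *a* ≥ 10 minutes.
- If the agent is not stopped before the last suture, *d* − *c* ≥ 0.
- The recorded surgery time therefore exceeds the recorded anaesthesia time by at least 10 minutes.

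**Rescue: first score taken through both readings.** Doses are those in item 6; the score range is 0 to 10.

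| First FLACC score | Reading A | Reading B, at that score |
|---|---|---|
| 0–3 | none | none |
| 4 | paracetamol | paracetamol |
| 5–10 | paracetamol and nalbuphine | paracetamol; nalbuphine only if pain or a score above 4 remains |

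Scores that trigger rescue are 4 to 10, or 7 values. Scores on which the readings part are 5 to 10, or 6 of those 7. This counts scale values, not children; it does not say how often the question will arise.

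**Outcomes that do not move.** Both readings start an analgesic at the first score of 4 or more, so time to first analgesic and the number of patients rescued are the same. Paracetamol at that first event is 10 mg/kg under both.

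**Size at the first rescue event only.** Each arm has 60 / 2 = 30 children. Let *k* be the number in an arm whose first rescue score is 5 to 10, and *p* the share of them whose pain persists after paracetamol. The protocol gives neither, so both are assumed. The arm-mean difference in nalbuphine between readings is 0.1 × (*k*/30) × (1 − *p*) mg/kg.

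| *k* (share of arm) | *p* = 0 | *p* = 0.5 | *p* = 1 |
|---|---|---|---|
| 6 (20%) | 0.02 | 0.01 | 0 |
| 15 (50%) | 0.05 | 0.025 | 0 |
| 24 (80%) | 0.08 | 0.04 | 0 |

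**Why this does not bound the total.** MEASUREMENTS, item 5 schedules FLACC at 15 and 30 minutes and then 2-hourly for 8 hours: 2 + 8/2 = 6 assessments. A later score above 4 raises the same question again, so a child's total could differ by more than 0.1 mg/kg. Early nalbuphine might also reduce later need and pull the other way. The table describes one first-rescue event per child and nothing beyond it.

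**The case against.** The strongest reply is that the rescue rule can be read as cumulative. Under reading B, a score still above 4 after paracetamol is already persisting pain, so the second clause would add almost nothing; only reading A gives both clauses work to do. That is a fair textual argument, and it makes reading A plausible. It does not compel it: the first sentence sends all scores of 4 or more to paracetamol without mentioning a second drug, and a stepwise reading of the next sentence remains natural. A request for clarification stands.

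It is also fair to say that the noise is conditional. If staff apply one reading throughout, there is no extra variation; the outcome simply depends on a convention that the protocol does not record.

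A reader might infer more than the document supports:

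- **Between-group bias.** The same rule governs both arms and the nurse scoring pain is blinded, so the text gives no ground for it.
- **Loss of power.** No standard deviation for analgesic consumption is given, so none can be derived.
- **A ceiling on total consumption.** The first-event figures are not one, and a zero difference when pain persists in every child also holds for the first event only.
- **Nalbuphine in place of paracetamol above 4.** The unqualified first sentence argues against this reading.

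On the durations, the reply is that they are descriptive and no stated outcome uses them. That is correct and limits the weight of the point, but the definitions are still wrong as written.

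**Conclusion.** Both faults hold, and both are minor. They are independent, and neither supports the other.

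The duration definitions are exchanged. Followed literally, both are reported under the wrong label, with surgery at least 10 minutes longer than anaesthesia. This assumes only that the inhaled agent is not stopped before the last suture.

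The rescue sentences do not settle the sequence of drugs at a first score of 5 to 10. The two readings differ by up to 0.1 mg/kg of nalbuphine at a first-rescue event, and total postoperative analgesic requirement inherits that dependence. Its size over the observation period cannot be bounded from the protocol.

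**What to change.** **Durations.** Exchange the two definitions in the protocol and the case-record form: duration of surgery takes the incision-to-suture interval, and duration of anaesthesia the interval from induction to discontinuation of the inhaled agent.

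**Rescue.** The sponsor must reconcile the two sentences in item 6 so that each FLACC score leads to one stated action and one stated sequence, at first and at later assessments. Which action and sequence is a matter for the clinical team.

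The cost is wording in the protocol and the case-record form. The sample size, visit schedule and list of outcomes do not change.

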Patients will be placed in lateral decubitus position. The area at the level of and 1-2 cm lateral to T10 over both sides of spine will be sterilized with 10% povidone-iodine and the probe will be placed in sterile gloves. After visualization of the erector spinae

muscle, the needle will be inserted proximally. After hydro dissection, the needle tip will be confirmed to be between the fascia of the erector spinae muscle group and the transverse process, the dilute solution of bupivacaine 0.25% at dose 0.4 ml/kg will be injected on each side.⁽¹⁶⁾ After the block patients will be placed in supine position and surgery will take place 10 minutes after injection.

Group CB:

After induction of general anaesthesia, the patient will be placed in left lateral decubitus position with the upper hip flexed at 90-degree angle. The needle insertion site will be sterilized using 10% povidone-iodine and the probe will be covered with sterile gloves. The sacral hiatus will be visualized using the ultrasound as two hyperechoic band like lines, the superior line being the sacrococcygeal ligament and the inferior line the dorsum of the pelvic surface of the sacrum. A “pop” or “give” is usually felt when the sacrococcygeal ligament is penetrated. A 22G needle will be introduced at a 45° angle. Cautious aspiration will be performed to rule out an inadvertent systemic or spinal needle location then patients will receive dilute solution of bupivacaine 0.25% at dose 1 ml/kg between the two sacral cornua while observing caudal epidural space dilation or turbulent flow with Doppler. Then, we will wait 10 minutes before the first surgical incision.⁽¹⁸⁾

Haemodynamic will be closely monitored. Failure of block will be defined as increase in heart rate and or mean arterial blood pressure (MAP) above 10% than baseline values at the beginning of surgery, intravenous fentanyl will be given at dose 0.5 ug/kg and patient will be excluded from the study and replaced by another patient. Methods to keep normothermia will be done via warmed iv fluids and forced air-warming blankets.

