At the end of surgery, O₂ 100% > 5 L/min will be continued after the discontinuation of sevoflurane. Once the patient shows adequate recovery from anaesthesia, oropharyngeal suction will be performed, and the LMA will be removed. Patients will be transferred to the post anaesthesia care unit (PACU) for monitoring of vital signs. Children will be considered ready for discharge from the PACU when being fully awake, stable vital signs for 30 min, no pain, no nausea or vomiting and the Modified Aldrete post-anesthesia score was ≥ 9 .

MEASUREMENTS

The following parameters will be measured:

1. Demographic data:

- Age.
- Sex.
- Weight.
- **Duration of surgery:** (time from the start of induction till discontinuation of the inhaled anaesthetics in minutes).
- **Duration of anaesthesia:** (from skin incision to final skin sutures in minutes).
- **Type of surgical procedure.**

2. Haemodynamic measurements:

- Heart rate (beats/min) using lead II electrocardiogram (ECG) waves.
- Mean arterial blood pressure: (MABP) in mmHg.
- Oxygen saturation.

They will be monitored and recorded at the following times:

- Pre-induction.
- Post-induction.
- Immediately after performing the block.
- At the start of surgical manipulation.
- Intraoperative every 10 minutes.
- At the end of the operation.

3. Time to Modified Aldrete score ≥ 9 .
4. PACU stay (min).
5. Postoperative pain: It will be assessed 15, 30 minutes in recovery room then every 2 hours the next 8 hours using FLACC Behavioural Pain Assessment Scale. Postoperative pain score will be assessed by a nurse blinded to the patient's anaesthetic management.⁽¹⁹⁾

FLACC Behavioural Pain Assessment Scale 5 parameters: Table (1)

1. Face.
2. Legs.
3. Activity.
4. Cry.
5. Consolability.

Table (1): FLACC Behavioural Pain Assessment Scale

Category	0 score	1 score	2 score
Face	No Particular expression or smile	Occasional grimace or frown; withdrawn, disinterested	Frequent to constant frown, clenched jaw, quivering chin
Legs	Normal position or relaxed	Uneasy, restless, tense	Kicking or legs drawn up
Activity	Lying quietly, normal position, moves easily	Squirming, shifting back and forth, tense	Arched, rigid, or jerking
Cry	No cry (awake or asleep)	Moans or whimpers, occasional complaint	Crying steadily, screams or sobs; frequent complaints
Consolability	Content, relaxed	Reassured by occasional touching, hugging, or being talked to; distractible	Difficult to console or comfort

Interpreting the Behavioural Score: Table (2)

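### Failed block is listed as a measured complication for the erector spinae arm only, while the exclusion-and-replacement rule removes it from the retained children in both arms, with no provision to count it

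*Protocol*

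**What the plan says.** The secondary aims in AIM OF THE WORK include "Incidence of any adverse effects", worded without reference to arm. The paragraph before that section says the comparison is meant to show, among other things, which block has fewer side effects.

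MEASUREMENTS opens with "The following parameters will be measured", and item 10 of that list covers side effects:

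- **10B, erector spinae technique:** after the complications common to any peripheral nerve block, "vascular puncture, pleural puncture, pneumothorax, and failed block are the primary complications".
- **10C, caudal technique:** "Epidural abscess, meningitis, post dural puncture headache, subdural injection, pneumocephalus, air embolism and back pain". These are seven items, and failed block is not one of them.

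Two other places give the same term a different role:

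- The exclusion criteria under PATIENTS end with "Block failure".
- The last paragraph of Block Procedure, after both group descriptions, gives the only definition: "Failure of block will be defined as increase in heart rate and or mean arterial blood pressure (MAP) above 10% than baseline values", assessed when surgery begins. The "patient will be excluded from the study and replaced by another patient". Nothing limits this rule to one arm.

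**The concern.** One event has two roles that do not fit together. It is a complication to be measured, and it is also a reason to take the child out of the study. If side effects are tabulated on the children who remain, those with the event have already left.

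The listing is also one-sided. The failure rule applies to both blocks, but the side-effect lists name failure for only one of them. An event named for one arm only cannot support a comparison between arms.

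What is at stake is a secondary aim. The trial asks whether erector spinae block may be an alternative to caudal block and which has fewer side effects, and how often each block fails bears on both questions. The rule could remove different numbers of children from the two arms, and no planned output would show it.

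**Working it through.** The protocol states no block-failure rate, so there is no figure to reproduce. The check has a textual part and an illustration.

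**Text, side by side**

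| Place | Erector spinae | Caudal |
|---|---|---|
| MEASUREMENTS, item 10 | failed block listed (10B) | failed block not listed (10C) |
| Block Procedure, failure rule | excluded and replaced | excluded and replaced |
| Exclusion criteria | block failure excludes | block failure excludes |
| Count of failures among replaced children | not provided for | not provided for |

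It follows that any child who meets the Block Procedure definition is not retained. The count of such failures among retained children is 0 in each arm.

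**Illustration**

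Inputs:

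- Total of 60 children (PATIENTS) and "Patients will be randomized into two equal groups", hence 60/2 = 30 retained per arm.
- Failure rate q: assumed to be 5%, 10% or 20%.
- Replacement: assumed to be within the same arm until 30 are retained. The protocol says only that another patient replaces the child.

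Formulas: expected failures before 30 retained = 30q/(1−q); chance of at least one failure before 30 retained = 1−(1−q)^30.

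| Assumed q | Expected failures replaced | Chance of at least one | Failures among 30 retained |
|---|---|---|---|
| 5% | 30 × 0.05/0.95 = 1.6 | 1−0.95^30 = 0.785 | 0 |
| 10% | 30 × 0.10/0.90 = 3.3 | 1−0.90^30 = 0.958 | 0 |
| 20% | 30 × 0.20/0.80 = 7.5 | 1−0.80^30 = 0.999 | 0 |

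**What the choice of denominator does** (Clopper–Pearson 95% intervals)

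- Retained children only: 0/30, upper limit 1−0.025^(1/30) = 11.6%.
- All children given the block, with 3 failures: 3/33 = 9.1% (1.9% to 24.3%).
- All children given the block, with 8 failures: 8/38 = 21.1% (9.6% to 37.3%).

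A table on retained children would show 0/30 with an interval that excludes 20%, even if 20% were the true rate. If the true rates were 5% in one arm and 20% in the other, about 1.6 and 7.5 children would be replaced. The retained sets would still read 0/30 and 0/30, and a difference of 15 percentage points would not appear.

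**The case against.** A reader might infer that failed block is impossible to observe, that its reported incidence must be zero, and that the caudal arm will report nothing. The protocol does not support any of these readings:

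- The event has to be seen in theatre to trigger the exclusion. The protocol does not forbid a tally of replaced children, and it states no denominator for adverse effects.
- The definition concerns the beginning of surgery, and item 10B does not refer to it. A child whose block proves inadequate later could be retained and counted.
- The secondary aim on adverse effects is neutral as to arm, and the failure rule detects caudal failures in the same way. They are only unnamed in the caudal list.

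Item 10B can also be read as a description of known hazards rather than a formal outcome definition. That has some force, since it gives no time point or denominator. But it stands in the numbered list of parameters to be measured and supplies content for a stated secondary aim.

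Two further objections stand in part. The point shares its root with the wider problem of excluding and replacing children after randomisation, although repairing the set used for pain scores would leave 10B and 10C mismatched. The sizes rest on assumed rates.

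That analysis details may be left to a statistical analysis plan does not answer the point. The conflict of roles and the one-sided list are already fixed in the protocol.

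**Conclusion.** The concern holds in a limited form. Failure by the Block Procedure definition is necessarily 0 among retained children in each arm, and the protocol neither provides for counting it among replaced children nor lists it for both arms. The textual conflict needs no assumption. The figure of about 1.6 to 7.5 uncounted failures per arm depends on assumed rates of 5% to 20%, replacement within the same arm, and 30 retained children per arm.

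The point affects one item of one secondary aim. It does not bear on the sample size. It should be corrected because the correction is cheap and the side-effect comparison is otherwise incomplete on an event central to the choice between the blocks.

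**What to change.** Reconcile the exclusion criteria, the failure rule in Block Procedure and MEASUREMENTS item 10, so that they agree on how a failed block is treated in the reporting. Specifically:

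- List block failure, by the Block Procedure definition, as one outcome recorded identically in both arms, in place of the mention under 10B alone.
- Use as denominator every child who received the allocated block, including those later replaced.
- Report number, percentage and exact 95% confidence interval per arm, and the between-arm difference.
- State separately whether a block that proves inadequate later in surgery is counted, and under what name.

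This changes reporting only and leaves clinical management as it is. It is best made together with any repair of the post-randomisation exclusion rule. The cost is a short wording change and one table row, with no extra children or procedures, because the event is already detected in theatre. The downside is that the reported adverse-effect incidence may look less favourable, and the between-arm estimate will be imprecise, as the width of the intervals for 3/33 and 8/38 shows.
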